3.5 Safety Assessment

Safety endpoints will be analysed in the Safety set.

3.5.1 Adverse Events (AEs)

Ocular and systemic AEs reported during the investigation will be coded using the MedDRA dictionary version 26.0 or higher.

Treatment-Emergent Adverse Event

An overview of TEAEs by treatment groups, separately for ocular and systemic TEAEs, will be provided for each of the following TEAE categorizations, in terms of the count and percentage of patients experiencing at least once such a TEAE:

- Any TEAE
- Any Serious TEAE
- TEAE leading to premature IMD discontinuation
- IMD-related TEAE
- IMD-related serious TEAE

[figure not shown]
A summary table by treatment groups, separately for ocular and systemic TEAEs, will be presented for each of the following TEAE categorizations, in terms of the count and percentage of patients experiencing at least once such a TEAE, as well as the number of TEAEs by SOC and PT:

[figure not shown]
- TEAEs leading to premature IMD discontinuation
- TEAEs by severity (Mild/Moderate/Severe/Missing if any)
- TEAEs by relationship to IMD (Not Related/Missing, if any/Possible/Probable/Causal Relationship)
- Serious TEAEs by relationship to IMD

A summary table by treatment groups, for ocular and systemic AEs altogether, will be presented for each of the following AE categorizations, in terms of the count and percentage of patients experiencing at least once such an AE as well as the number of AEs by SOC and PT:

- Any Non-Serious TEAE
- Any Non-Serious TEAE, with PT occurring for at least 5% of the patients in any of the treatment groups
- Any Serious AE

Listings will be presented specifically for TEAEs, separately for ocular and systemic TEAEs.

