7.2.2 Safety Analyses

Safety endpoint will be analysed in the Safety set.

Ocular and systemic adverse events (AEs)

Ocular and systemic AE reported during the investigation will be coded using the Medical Dictionary for Regulatory Activities (MedDRA dictionary).

Summary tables will be performed on TEAEs.

Ocular and systemic TEAEs will be analysed separately on the basis of the localisation as recorded by the investigator in the CRF.

TEAEs are AEs that occurred after the first IMD instillation. AEs that occurred the day of the first IMD instillation will be reviewed during a blind review meeting to decide if they have to be considered as TEAE or not.

Separate descriptions of ocular and systemic TEAEs will be performed by treatment group:

- Number and percentage of patients experiencing at least one AE, SAE, IMD-related AE, and AE leading to premature investigation IMD discontinuation.
- Number and percentage of patients experiencing at least one AE, as well as the number of AEs, by SOC and PT. The same summary table will be performed for SAEs, IMD-related AEs, IMD-related SAEs and AEs leading to premature investigation IMD discontinuation.
- Number and percentage of patients with AEs, by SOC, PT and severity.
- Number and percentage of patients with AEs, by SOC, PT and relationship with IMD.

[figure not shown]
Documented list of individual data concerning TEAEs will be performed.

Separated descriptions of ocular and systemic during the run-in period will be performed overall:

- Number and percentage of patients experiencing at least one TEAE, as well as the number of TEAEs, by SOC and PT. The same summary table will be performed for SAEs (if any), and TEAEs related to run-in treatment.

Individual patient data listings of TEAEs will be performed for overall AEs, SAEs and IMD-related SAEs, separately for ocular and systemic AEs.

[figure not shown]
List will also be performed on non-TEAEs (before the first IMD instillation).

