14. ADVERSE EVENTS, ADVERSE DEVICE EFFECTS AND DEVICE DEFICIENCIES

14.1 DEFINITION OF ADVERSE EVENT (AE) AND ADVERSE DEVICE EFFECT (ADE)

Adverse Event (AE): Any untoward medical occurrence, unintended disease or injury or untoward clinical signs (including abnormal laboratory finding) in subjects, users or other persons whether or not related to the IMD.

NOTE:

- This definition includes events related to the IMD or the comparator
- This definition includes events related to the procedures involved
- For users or other persons, this definition is restricted to events related to the use of the IMD or comparator.

Adverse device effect (ADE): AE related to the use of an IMD.

NOTE:

- This definition includes AEs resulting from insufficient or inadequate instructions for use, deployment, implantation, installation or operation, or any malfunction* of the IMD;
- This definition includes any event resulting from use error or from intentional misuse of the IMD.
- This includes comparator if the comparator is a medical device.

*Malfunction is defined as a failure of an IMD to perform in accordance with its intended purpose when used in accordance with the instructions for use or CIP.

Treatment-emergent AE (TEAE): AE that occurs or that worsens in severity after at least one dose of IMD has been administered/applied.

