14.4 RECORDING AES

AEs recording and reporting will extend from signing of informed consent until the final visit. If the investigator is aware of an AE occurring within one month after final investigation visit and that he considers there is a causal relationship with the IMD, the AE should be recorded in the e-CRF.

The investigator shall:

- a) Record all AEs, regardless of the relationship to IMD, in the e-CRF, together with an assessment.
- b) Report to the Sponsor, without unjustified delay, all serious AEs; this information shall be promptly followed by detailed written reports.
- c) Supply the Sponsor, upon Sponsor's request, with any additional information related to the safety reporting of a particular event.

All AE reports should contain: a brief description of the event (diagnosis, localisation ...) date and time of onset (if needed), duration (hours or days), intensity of symptoms (severity), treatment required, relationship with IMD and CIP procedure, action taken with the IMD, outcome, date and time of resolution and whether the event is classified as serious.

If there is a worsening of a medical condition that was present before starting the clinical investigation, this should be considered as a new AE and a complete evaluation should be recorded.

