3.2 Analysis Sets

3.2.1 *Enrolled Set*

All patients who have signed the informed consent form and for whom the inclusion visit has been recorded in the eCRF.

3.2.2 *Safety Set*

All enrolled patients, having received at least one dose of IMD and analysed as treated.

The safety set will be the primary population for safety analysis.

3.2.3 *Intent-To-Treat (ITT) Set*

All randomised patients and analysed as randomised.

[figure not shown]
3.2.4 *Full Analysis Set (FAS)*

All randomised patients, having received at least one dose of IMD, with at least one baseline and one post-randomisation performance assessment and analysed as randomised.

The FAS will be the primary population for performance analysis.

3.2.5 *Per Protocol (PP) Set*

Subset of the FAS including patients without any major CIP deviations likely to seriously affect the primary [REDACTED] outcome of the study

Deviations from the CIP will be defined and assessed as “minor” or “major” in cooperation with the Sponsor during a blind review meeting before the database lock. A list of patients with major deviations from the CIP leading to exclusion from the PP set will be finalized prior to unblinding the randomised treatment assignments.

The PP set will be considered as secondary population and will be used for sensitivity analyses of the primary [REDACTED] endpoint. Patients will be analysed as treated.

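### One by-arm table in SAP 3.5.1 counts all serious AEs beside rows limited to TEAEs, so read literally it places pre-dose serious events under an IMD arm

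*SAP*

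**What the plan says.** The table at issue is the last one in SAP 3.5.1. It is introduced with "A summary table by treatment groups, for ocular and systemic AEs altogether, will be presented for each of the following AE categorizations", and it gives patient and event counts by SOC and PT. Its first two categories are non-serious TEAEs, and non-serious TEAEs with a PT frequency of at least 5% in either arm. The third is "Any Serious AE".

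The same section has other by-arm output on serious events, all limited to TEAEs and all split into ocular and systemic. The overview has "Any Serious TEAE" and a row for serious TEAEs related to the IMD. The SOC/PT tables include "Serious TEAEs by relationship to IMD".

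Protocol 14.4 sets the collection window: "AEs recording and reporting will extend from signing of informed consent until the final visit". Protocol 14.1 defines a TEAE as an "AE that occurs or that worsens in severity after at least one dose of IMD has been administered/applied". Safety output uses the Safety set (SAP 3.5), defined in SAP 3.2.2 as "All enrolled patients, having received at least one dose of IMD and analysed as treated".

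Protocol 7.2.2 states "Summary tables will be performed on TEAEs". It describes run-in events overall rather than by arm, asks for the same summary for SAEs, and lists non-TEAEs. The visible text of SAP section 6 gives two changes from the protocol: the added Enrolled set, and the dropping of some SAE listings. Neither concerns the scope of this row.

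**The concern.** Both the row and its lead-in say AE, where the two preceding lead-ins in SAP 3.5.1 say TEAE. A programmer who follows the text would include every serious AE of a Safety-set patient, whenever it occurred after consent. An event on Hydrabak, or between consent and Visit 1, would then appear under a product the patient had not yet used.

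In the visible text this is also the only by-arm count of serious events that combines ocular and systemic. A combined patient count for serious TEAEs cannot be recovered by adding the separate tables, because a patient with both kinds would be counted twice. Serious events are likely to be few in a trial of this size and length, so one event could visibly change the comparison in this table, and a reader could find it hard to reconcile with the TEAE tables.

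**Working it through.** The documents state no figure on this point, so the main check is to follow one event through the definitions.

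1. A patient consents, starts Hydrabak and has a serious event in the run-in. It is recorded, because collection starts at consent (Protocol 14.4).
2. The patient is later randomised and takes the IMD, so belongs to the Safety set under the arm received (SAP 3.2.2).
3. The event began before any IMD dose. Unless it worsens after dosing, it is not a TEAE (Protocol 14.1).
4. The planned outputs treat it as follows:

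| Output | By arm? | Event counted? |
|---|---|---|
| Overview, serious TEAEs (SAP 3.5.1) | yes, ocular and systemic separate | no |
| Overview, IMD-related serious TEAEs (SAP 3.5.1) | yes, separate | no |
| SOC/PT, serious TEAEs by relationship (SAP 3.5.1) | yes, separate | no |
| SOC/PT, combined, serious AEs (SAP 3.5.1) | yes, combined | **yes, read literally** |
| Run-in summary (Protocol 7.2.2) | no, overall | yes |

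An AE on the day of first instillation that blind review (Protocol 7.2.2) judges not treatment-emergent would, if serious, also be counted in the fourth row. A patient with a run-in event who is never dosed is outside the Safety set and is counted under no arm.

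**Share of recording time before the IMD.** Inputs: run-in 7 to 10 days and treatment 36 to 39 days (SAP 2.2.1); consent up to 7 days before Visit 1 (Protocol 6.1.4). Share = pre-dose days / (pre-dose days + treatment days).

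- Shortest run-in, longest treatment: 7/(7 + 39) = 7/46 = 15%
- Longest run-in, shortest treatment: 10/(10 + 36) = 10/46 = 22%
- The same, with consent 7 days before Visit 1: 17/(17 + 36) = 17/53 = 32%

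**Chance that the row is affected at all.** The documents give no SAE rate, so the rate r per patient per 30 days is an assumption, taken from 0.2% to 1%. With d pre-dose days, p = 1 − (1 − r)^(d/30). The expected number per arm of 125 is 125p, and the chance of at least one such event among 250 is 1 − (1 − p)^250. For r = 0.5% and d = 7, p = 1 − 0.995^(7/30) = 0.00117, which gives 0.146 per arm and a 25% chance.

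| Assumed r | d = 7 | d = 10 | d = 17 |
|---|---|---|---|
| 0.2% | 0.058; 11% | 0.083; 15% | 0.142; 25% |
| 0.5% | 0.146; 25% | 0.209; 34% | 0.355; 51% |
| 1% | 0.293; 44% | 0.418; 57% | 0.710; 76% |

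Each cell gives expected events per arm, then the chance of at least one in 250. The cells assume that every affected patient goes on to be dosed, so they err on the high side. Even so, fewer than one event per arm is expected.

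**The case against.** The strongest reply is that this is loose wording. The row stands under a sub-heading on treatment-emergent events, and the visible safety endpoint in SAP 2.3.3 is TEAEs. The protocol is no stricter: in 7.2.2 the bullets under the TEAE descriptions say AE and SAE, and the run-in bullets say TEAE for events that cannot be treatment-emergent. Gaps also interrupt SAP 3.5.1, and the programming specifications are a separate document (SAP section 7), so a rule assigning events to study periods may exist out of view. This stands as a reason to be cautious about what the sponsor intends. It does not make the text right: the row and its lead-in both say AE, and a by-arm table should not depend on the programmer's guess.

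A reader might infer that the SAP has replaced serious TEAEs by all serious AEs, leaving no treatment-emergent comparison of the arms. The documents do not support that, because three other by-arm outputs in the same section count serious TEAEs.

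A reader might also take 15% to 32% as the share of events in the row that pre-date the IMD. That does not follow either. It is a share of time and becomes a share of events only at a constant rate with every affected patient later dosed. Eligibility is checked again at Visit 2, and patients judged at significant risk are withdrawn (Protocol 6.3.3), so some would never be dosed. The denominator also omits IMD-related events that may be recorded up to one month after the final visit (Protocol 14.4). The 32% combines the earliest consent, the longest run-in and the shortest treatment.

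Finally, almost all pre-dose time is before randomisation, so these events balance between arms in expectation, and the visible safety output is descriptive. This is correct and limits the severity. It does not prevent a chance imbalance when counts are very small.

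**Conclusion.** Wrong as written (minor). On its literal wording, one descriptive table counts pre-dose serious events of dosed patients under the IMD arm. That departs from Protocol 7.2.2, and the visible SAP section 6 does not declare it. The row matters somewhat more than its place suggests, because it is the only visible by-arm count that combines ocular and systemic serious events.

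The size is small: fewer than one such event per arm expected at any assumed rate up to 1% per 30 days, and no systematic bias between arms. The discrepancy with the TEAE tables arises only if at least one such event occurs. The conclusion rests on reading the row as it stands and on no hidden text restricting it. The primary analysis, sample size and alpha are unaffected.

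**What to change.** In SAP 3.5.1, restrict the serious row of the combined table to serious TEAEs, and make the lead-in say TEAE to match the two before it. By definition this removes pre-dose events from the by-arm count.

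Carry into the SAP the overall run-in summary that Protocol 7.2.2 already requires, including its SAE table, and report there the serious events with onset before the first IMD instillation. State that it covers the time from consent, so that an event between consent and Visit 1 has a place.

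If the sponsor wants all serious AEs in this table by design, show those before the first dose separately and declare the change from the protocol in SAP section 6.

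The cost is a one-word change to the row, a matching edit to the lead-in, and one small table that the protocol already calls for.

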4 DATA SAFETY MONITORING BOARD

No Data Safety Monitoring Board (DSMB) is planned for this study.

[figure not shown]
5 ANALYSIS TIMING

[figure not shown]
5.1 Draft Analysis/Blinded Data Reviews

Draft analysis Tables, Figures, and Listings (TFLs) for blinded data reviews will be provided prior to the scheduled database lock for final review.

5.2 Interim Analysis

[figure not shown]
No interim analysis is planned.

[figure not shown]

6 CHANGES FROM CIP-SPECIFIED STATISTICAL ANALYSES

The following changes from the protocol-specified statistical analyses have been made:

- Addition of the Enrolled set

- Individual patient data listings, separately for ocular and systemic AEs, are not provided for SAEs and IMD-related SAEs.

7 PROGRAMMING SPECIFICATIONS

Analyses will be performed using [REDACTED] [REDACTED] [REDACTED] [REDACTED] [REDACTED]. Detailed Programming Specifications will be provided in a separate document. All Derived Datasets and TFL programs will be validated according to [REDACTED] SOP [REDACTED]
